5.3.2.2 Blood sampling for pharmacokinetic analysis (BI 730357 trough samples)

For quantification of BI 730357 plasma concentrations 2.7 mL of blood will be taken from an antecubital of forearm vein into a separate K₂-EDTA (dipotassium ethylenediaminetetraacetic acid as anticoagulant) blood drawing tubes at the times indicated in the [Flow Chart](#). Blood will be withdrawn by means of either an indwelling venous catheter or by venipuncture with a metal needle.

The EDTA-anticoagulated blood samples will be centrifuged for approximately 10 min at approximately 2000 x g to 4000 x g and at 4 to 8 °C. Two plasma aliquots will be obtained and stored in polypropylene tubes. The first aliquot should contain at least 0.5 mL of plasma.

The process from blood collection until transfer of plasma aliquots into the freezer should be completed within 120 min with interim storage of blood samples at room temperature and without exposition to direct sunlight.

[figure not shown]
The time each aliquot was placed in the freezer will be documented. Until transfer on dry ice to the analytical laboratory, BI 730357 aliquots will be stored upright at approximately -20°C or below at the trial site. The second aliquot will be transferred to the analytical laboratory after the bioanalyst has acknowledged safe arrival of the first aliquot. At the analytical laboratory, the plasma samples will be stored at about -20°C or below until analysis.

At a minimum, the sample tube labels should list BI trial number, subject number, visit, planned sampling time, and the analyte (e.g. 'BI 730357'). Further information such as matrix may also be provided.

5.3.2.3 Urine sampling for pharmacokinetic analysis

A blank urine sample will be collected before administration of trial medication (see Flow Chart) and aliquots will be retained to check for analytical interference. All urine voided during the sampling intervals indicated in the Flow Chart will be collected in 2 L polyethylene (PE) containers and stored at room temperature. Subjects are told to empty their bladders at the end of each sampling interval.

The urine weight/volume for each collection interval will be documented (however, no correction for the specific gravity of urine is done, i.e. 1 L is defined to be equal to 1 kg). Aliquots will be stored in polypropylene (PP) tubes for bioanalytical measurement. In case more than one collection container is used in an interval, the contents of all containers are to be mixed before aliquots are prepared. Mixing should be done by transferring the entire content of all collection containers into a single PE/PP or glass container, and stirring the mixed fractions for about 1 min (manually or using a stir bar or other stirring device made of PE, PP, Teflon or glass).

For each sampling interval or time point seven urine aliquots of at least 2 mL will be obtained (4 primaries, 2 back-ups 

For the 4 primaries and the 2 back-ups: Until transfer on dry ice, the urine samples will be stored at about -20°C or below at the trial site. For all treatment periods, the primary aliquots will be sent to the bioanalytical laboratory first. They will be sent in two shipments; the second shipment will be sent only after the bioanalytical laboratory has acknowledged safe arrival of the first shipment. At the bioanalytical laboratory, the primary aliquots will be stored at about -20°C or below until analysis.

The back-up aliquots will only be transferred to the analytical laboratory analysing cocktail components if needed (primary aliquots are foreseen for these analyses). In any case, back-up aliquots will only be shipped from the clinical site once the bioanalyst has acknowledged safe arrival of the primary aliquots at the analytical laboratory.

At minimum, the sample tube labels should list the following information: BI trial number, subject number, visit number, aliquot, and planned collection interval or time point, as applicable. Further information, such as matrix, may also be provided.

The aliquot names are planned as follows:

- “A1 - PKU D” = primary for digoxin
- “A2 - PKU F” = primary for furosemide
- “A3 - PKU M” = primary for metformin
- “A4 - PKU R” = primary for rosuvastatin

5.3.2.4 Further investigations

[figure not shown]
After completion of the analysis of plasma and urine samples for concentrations of digoxin, furosemide, metformin, and rosuvastatin, the plasma and urine samples (including back-ups and left-over sample volumes from pre-specified analyses) may be used as follows:

[figure not shown]
- For further methodological investigations, e.g. for stability testing, assessment of metabolites. However, only data related to the analyte and/or its metabolite(s) including anti-drug antibodies (if applicable) will be generated by these additional investigations

- For analyses of the concentrations of BI 730357 and its metabolites

Results of further investigations are not planned to be part of the trial report; however, results of further investigations may be part of the trial report, if required.

The study samples will be discarded after completion of the additional investigations, but not later than 5 years after the CTR is archived.

[figure not shown]

5.4.2 Pharmacodynamic biomarkers

Not applicable.

5.5 BIOBANKING

Not applicable.

5.7 APPROPRIATENESS OF MEASUREMENTS

All measurements performed during this trial are standard measurements and will be performed in order to monitor subjects' safety and to determine pharmacokinetic parameters in an appropriate way. The scheduled measurements will allow monitoring of changes in vital signs, standard laboratory values, and ECG parameters that might occur as a result of administration of trial medication. The safety assessments are standard, are accepted for evaluation of safety and tolerability of an orally administered drug, and are widely used in clinical trials. The pharmacokinetic parameters and measurements outlined in Section [5.3](#) are generally used assessments of drug exposure. The biomarkers outlined in Sections [5.4](#) are of exploratory nature, only.

6. INVESTIGATIONAL PLAN

6.1 VISIT SCHEDULE

Exact times of measurements outside the permitted time windows will be documented. The acceptable time windows for screening and the end of trial examination are provided in the [Flow Chart](#).

Study measurements and assessments scheduled to occur 'before' trial medication administration are to be performed and completed within a 2h-period prior to the next trial drug administration, if not indicated otherwise in the FlowChart.

For ambulatory administration of BI 730357 prior to Day -1 of Visit 3, a time window of \pm 70 minutes will be allowed.

Following administration of trial drugs in Visits 2 and 3, the acceptable deviation from the scheduled time for vital signs, ECG, and laboratory tests will be \pm 30 min on Day 1 and \pm 45 minutes from 28 hours onwards.

The acceptable deviation from the scheduled time for all meals on Day 2 in Period 1 is \pm 2 h to allow, that subjects may have their meal together.

If scheduled in the Flow Chart at the same time as a meal, blood sampling, vital signs, and 12-lead ECG recordings have to be done first. Furthermore, if several measurements including venepuncture are scheduled for the same time, venepuncture should be the last of the measurements due to its inconvenience to the subject and possible influence on physiological parameters.

For planned blood sampling times and urine collection intervals, refer to the Flow Chart. While these nominal times should be adhered to as closely as possible, the actual sampling times will be recorded and used for the determination of pharmacokinetic parameters.

For cocktail PK blood sampling on Day 7 of Visit 2 and Days 6 and 8 of Visit 3, respectively, a time window of \pm 60 minutes will be allowed.

If a subject misses an appointment, it will be rescheduled if possible. The relevance of measurements outside the permitted time windows will be assessed no later than at the Report Planning Meeting.

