			-1:30	07:30	Standardized breakfast							
			0:00	09:00	Cocktail dosing				▲			x
			0:20	09:20				x				
			0:40	09:40				x				
			1:00	10:00				x		x	x	x
			1:30	10:30				x				
			2:00	11:00	240 mL fluid intake			x		x	x	x
			2:30	11:30				x				
			3:00	12:00				x				
			4:00	13:00	240 mL fluid intake, thereafter lunch ³			x	+	x	x	x
			5:00	14:00				x				
			6:00	15:00				x				
			8:00	17:00	Extended snack ³ (voluntary)			x	+			x
			10:00	19:00				x				
			10:30	19:30	Standardized dinner							
			12:00	21:00				x	+			x
			2	24:00	09:00	Breakfast ³	B	x	+	x	x	x
				28:00	13:00	Lunch						x
		32:00	17:00	Snack (voluntary)								
		34:30	19:30	Dinner								
		36:00	21:00			x	+			x		
	3	48:00	09:00	Discharge, breakfast (voluntary) ³		x	▼			x		
	4	71:00	08:00	Ambulatory visit		x				x		
	5	95:00	08:00	Ambulatory visit		x				x		
	7	143:00	08:00	Ambulatory visit		x				x		

- Subject must be informed and written informed consent obtained prior to starting any screening procedures. Screening procedures include physical examination, check of vital signs, ECG (including rhythm stripe over 15 min), safety laboratory (including drug screening), demographics (including determination of body height and weight, smoking status and alcohol history), pregnancy test in females, relevant medical history, concomitant therapy and review of inclusion/exclusion criteria. Pharmacogenetic samples will be collected if needed.
- The time is approximate; the procedure is to be performed and completed within 3 h prior to study drug administration.
- If several actions are indicated at the same time point, the intake of meals will be the last action.
- Only urine drug screening, alcohol breath test and pregnancy test in females.
- AEs and concomitant therapies will be recorded throughout the trial, but will be specifically asked for at the time points indicated in the Flow Chart above.
- A blank urine sample (x) is to be obtained prior to administration of trial medication. Other urine samples are to be collected over the stated post-dose intervals (◀—|—|—▶) 0-4, 4-8, 8-12, 12-24, 24-36 and 36-48 h.
- Letters A and B define different sets of safety laboratory examinations (for details refer to Section 5.2.3).

FLOW CHART – TREATMENT TEST

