			10:30	19:30	Standardized dinner									
			11:00	20:00	Dosing BI 730357					X ⁸				X
			12:00	21:00				X			+			X

[figure not shown]
FLOW CHART – Treatment Test, continued

Period	Visit	Day	Planned time (relative to cocktail administration) [h:min]	Approximate clock time of actual day [h:min]	Event and comment	Safety laboratory ⁹	PK blood, cocktail components	PK blood, BI 730357	PK urine, cocktail components ^{7, 10}	12-lead ECG	Vital signs (BP, PR)	Questioning for AEs and concomitant therapy ⁶		
2	3	2	22:30	07:30	Standardized breakfast									
			23:00	08:00	Dosing BI 730357			x ⁸					x	
			24:00	09:00		B	x		+	x	x	x		
			28:00	13:00	Lunch									x
			32:00	17:00	Extended snack ³ (voluntary)									
			34:30	19:30	Standardized dinner									
			35:00	20:00	Dosing BI 730357									x
			36:00	21:00			x		+					x
		3	46:30	07:30	Standardized breakfast									
			47:00	08:00	Dosing BI 730357									x
			48:00	09:00	Discharge		x		▼					x
			58:00	19:00	Ambulatory visit, standardized dinner									x
		4	58:30	19:30	Dosing BI 730357									x
			70:00	07:00	Ambulatory visit, standardized breakfast									
			70:30	07:30	Dosing BI 730357									x
			71:00	08:00			x							
			82:00	19:00	Ambulatory visit, standardized dinner									
		5	82:30	19:30	Dosing BI 730357									x
			94:00	07:00	Ambulatory visit, standardized breakfast									
			94:30	07:30	Dosing BI 730357									x
			95:00	08:00		B	x					x		
			106:00	19:00	Ambulatory visit, standardized dinner									
			106:30	19:30	Dosing BI 730357									x
		6	118:00	07:00	Ambulatory visit, standardized breakfast									
			118:30	07:30	Dosing BI 730357									x
			119:00	08:00			x							
			130:00	19:00	Ambulatory visit, standardized dinner									
			130:30	19:30	Dosing BI 730357									x
8	167:00	08:00	Ambulatory visit		x						x			
FU	4	14-22			End of trial (EoTrial) examination ⁴	C			x	x	x			

- [For footnote 1 see [Flow Chart of Treatment Reference](#)]
- The time is approximate; the procedure is to be performed and completed within 3 h prior to first drug administration.
- If several actions are indicated at the same time point, the intake of meals will be the last action.
- End of trial examination includes physical examination, vital signs, ECG, safety laboratory, pregnancy test in females, recording of AEs and concomitant therapies.
- Only urine drug screening, alcohol breath test and pregnancy test in females

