4.1.4 Drug assignment and administration of doses for each subject

This trial is a non-randomised 2-period fixed-sequence study. All subjects will receive the two treatments in a fixed sequence (Reference always followed by Test). The treatments to be evaluated are outlined in Table 4.1.4: 1 below.

[figure not shown]
Table 4.1.4: 1 Dosage and treatment schedule

Treatment	Substance	Formulation	Unit strength	Dosage	Total daily dose
R (cocktail)	Digoxin	Tablet	0.25 mg	1 tablet as single dose	0.25 mg
	Furosemide	Oral solution	10 mg/mL	0.1 mL (1 mg) as single dose	1 mg
	Metformin	Oral solution	1000 mg/5mL	0.05 mL (10 mg) as single dose	10 mg
	Rosuvastatin	Film-coated tablet	10 mg	1 tablet as single dose	10 mg
T	BI 730357	Film-coated tablet	100 mg	3 tablets (300 mg) bid for 13 days on Day 1 the morning dose is given 1 h prior to the cocktail	600 mg
	Digoxin	Tablet	0.25 mg	1 tablet as single dose	0.25 mg
	Furosemide	Oral solution	10 mg/mL	0.1 mL (1 mg) as single dose	1 mg
	Metformin	Oral solution	1000 mg/5mL	0.05 mL (10 mg) as single dose	10 mg
	Rosuvastatin	Film-coated tablet	10 mg	1 tablet as single dose	10 mg

The investigator (or authorised designee) will administer the trial medication as an oral dose together with about 240 mL of water (BI 730357) or 280 ml (for the cocktail) to subjects who are in standing position. For drug administration, the so-called four-eye principle (two-person rule) should be applied. For this, one authorised employee of the trial site should witness the administration of trial medication, and – if applicable – its preparation (e.g. reconstitution), if correct dosage cannot be ensured otherwise.

Fed conditions

A standardized meal (bread roll with butter, cheese and/or sliced sausage) will be served 30 min before each BI 730357 administration. The subjects must completely consume the meal prior to drug intake. To assure comparable conditions for the cocktail administration, the standardised meal will be served also in the Reference treatment 90 min prior to the planned dosing of the cocktail (the meal is to be consumed within 30 min).

Thereafter, complete drug administration is assumed.

All components of the cocktail should be administered within 2 minutes.

After cocktail administration (in R and T)

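### The 24 h vital signs follow a standardised breakfast in Test but precede breakfast in Reference, so their descriptive comparison mixes a meal effect with BI 730357

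*Protocol*

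**What the plan says.** **Test, Day 2 (Flow Chart, Treatment Test, continued).** The rows before the 24 h assessments read "22:30 07:30 Standardized breakfast" and "23:00 08:00 Dosing BI 730357". Vital signs, ECG, lab B and the PK sample follow at 24:00.

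**Reference, Day 2 (Flow Chart, Treatment Reference).** The meal is in the same row as the 24 h assessments: "24:00 09:00 Breakfast ³". Its footnote 3 sets the order: "If several actions are indicated at the same time point, the intake of meals will be the last action". The last scheduled meal before that is on Day 1: "10:30 19:30 Standardized dinner".

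**Day 1, both periods (Protocol 4.1.4, Fed conditions).** Food is matched on purpose for the cocktail dose: "the standardised meal will be served also in the Reference treatment 90 min prior to the planned dosing of the cocktail". There is no corresponding text for Day 2.

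**Tolerances (Protocol 6.1).** "The acceptable deviation from the scheduled time for all meals on Day 2 in Period 1" is ±2 h. The section then says that blood sampling, vital signs and ECG scheduled in the Flow Chart together with a meal come before the meal.

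**Analysis.** Protocol 7.3.4 plans a descriptive comparison of treatments. SAP 6.7 summarises vital signs by planned time point and uses the last value before the Period 1 cocktail as baseline for every on-treatment phase. SAP 7.8.3 adds change from baseline.

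**The concern.** The protocol equalises food for the Day 1 readings but not for the 24 h reading. Every Test subject is due to be measured soon after a meal and every Reference subject before one. The sequence is fixed, so food state at 24 h coincides completely with treatment, and no analysis of these data can separate the two. A reader of the vital-sign table who sees pulse or blood pressure shift at 24 h in Test could attribute to BI 730357, or to its combination with the cocktail, what a breakfast produced. A meal effect could equally mask a drug effect in the other direction. Both periods share only four post-cocktail vital-sign times, and 24 h is the last of them.

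**Working it through.** The plan gives no figure on this point, so there is none to reproduce. The check uses differences of planned times in the two Flow Charts, all relative to cocktail administration.

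**Inputs**
- Test: breakfast 22:30, BI 730357 23:00, vital signs 24:00.
- Reference: dinner 10:30, vital signs 24:00, breakfast 24:00 (last action).
- Day 1, both periods: breakfast -1:30; vital signs at 1:00, 2:00 and 4:00 (Test also at 8:00).
- Period 1 baseline: nominally -2:00. The Flow Chart calls this time approximate.

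**Time since food at 24 h**
- Test: 24:00 - 22:30 = 1.5 h after breakfast, and 24:00 - 23:00 = 1.0 h after BI 730357.
- Reference: 24:00 - 10:30 = 13.5 h after dinner, with breakfast still to come.

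The 1.5 h is nominal. Section 6.1 gives ±30 min for vital signs on Day 1 and ±45 min from 28 h onwards, and nothing explicit for 24 h. If ±30 min is assumed, the Test gap is 1.0 to 2.0 h; if ±45 min, 0.75 to 2.25 h. Either way the Test reading follows the meal.

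**Time since food on Day 1, both periods**
- 1 h: 1:00 - (-1:30) = 2.5 h.
- 2 h: 2:00 - (-1:30) = 3.5 h.
- 4 h: 4:00 - (-1:30) = 5.5 h.

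These three times are matched. Of the four times common to both periods (1, 2, 4 and 24 h), only 24 h is not.

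**What this does to the summary**

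The nominal baseline at -2:00 is 0.5 h before the -1:30 breakfast. The 24 h change from baseline is therefore unfed minus unfed in Reference, and fed minus unfed in Test. Let B be the common baseline, and T24 and R24 a subject's 24 h readings in Test and Reference:

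(T24 - B) - (R24 - B) = T24 - R24

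The baseline cancels and the food difference does not. If a meal shifts the reading by m, all of m enters this difference. The documents give no value for m. Purely as an assumption, if breakfast raises pulse by 2 to 10 bpm at that interval, the contrast moves by the same 2 to 10 bpm.

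**Does the ±2 h window matter?**

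Taken alone, it would let the Reference breakfast fall from 24:00 - 2:00 = 22:00 to 24:00 + 2:00 = 26:00, which is 07:00 to 11:00. The ordering rule in the same section and footnote 3 both put the 24 h measurements before the breakfast scheduled with them. Read together, breakfast may move only within the time after the measurements.

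**The case against.** The strongest reply is that the asymmetry follows from the regimen. Section 4.1.4 requires a meal before each BI 730357 dose, Reference has no Day 2 dose, and the stated purpose of matching is comparable conditions for cocktail administration, which Day 1 achieves. That is a fair account of how the difference arose. It does not remove the effect on a 24 h comparison that the SAP will tabulate.

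It can also be said that the safety analysis is descriptive, that clinically relevant vital-sign changes are reported as AEs anyway, and that a fixed sequence carries any period effect as well, so matching breakfast would not make the 24 h contrast a clean estimate of the BI 730357 effect. All of this stands and limits the weight of the point. Matching still removes one known source of difference.

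A reader might infer more than the documents support:

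- **That the ±2 h window lets Reference subjects be fed or fasted at 24 h.** It does not. A Reference subject given breakfast before the 24 h measurements would be a deviation from the ordering rule.
- **That an ECG comparison is confounded.** SAP 7.8.4 plans no separate ECG listing or analysis; relevant findings are reported as AEs.
- **That lab B is compromised.** Protocol 5.2.3 allows lab B under non-fasted conditions, and its panel does not include glucose.
- **That 24 h is the last vital-sign and ECG assessment in both periods.** In Test, the end-of-trial examination follows and includes both.

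**Conclusion.** The point holds for the 24 h vital signs. By the Flow Charts they are taken nominally 1.5 h after a standardised breakfast in Test and about 13.5 h after the last scheduled meal in Reference, for all 15 planned subjects. The descriptive Test-versus-Reference comparison at that time mixes a meal effect with BI 730357.

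The consequence is minor: one of four shared post-cocktail times, in a summary without hypothesis tests. Nothing here affects the primary or secondary PK endpoints. The conclusion assumes that sites follow the planned times and the ordering rule. The size of any meal effect is unknown from the documents, and the 2 to 10 bpm range only illustrates how such an effect would carry through.

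**What to change.** In the Reference Flow Chart, move the Day 2 breakfast from 24:00 to 22:30 (07:30) and make it the same standardised breakfast as in Test.

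In Section 6.1, exempt that breakfast from the ±2 h meal tolerance. The exemption is needed because, once moved, the breakfast no longer shares a row with the measurements and the ordering rule no longer fixes its place. With ±2 h around 22:30 it could fall anywhere from 20:30 to 24:30, on either side of the 24 h reading. Lunch, snack and dinner can keep the tolerance.

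The cost is one meal moved by 1.5 h for subjects already in house, and two lines in an amendment. The small downside is less freedom for a communal breakfast that day.

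If the schedule can no longer change, state in the trial report, beside the vital-sign tables, that the 24 h readings differ in food state between periods.

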6.2 DETAILS OF TRIAL PROCEDURES AT SELECTED VISITS

6.2.1 Screening

After having been informed about the trial, all subjects will provide written informed consent in accordance with GCP and local legislation prior to enrolment in the study.

For information regarding laboratory tests (including drug and virus screening), ECG, vital signs, and physical examination, refer to Sections [5.2.3](#) to [5.2.5](#).

6.2.2 Treatment periods

Each subject is expected to participate in 2 treatment periods (Days -1 to 7 in period 1 and Days -7 to Day 8 in Period 2). In the 2nd treatment period ambulatory dosing of BI 730357 (300 mg bid) starts on Day -7 to achieve steady state of the perpetrator drug. [REDACTED]

[REDACTED] In the 2nd treatment period twice daily dosing of BI 730357 is continued until Day 6.

In the evening of Day -1 of each treatment period, study participants will be admitted to the trial site and kept under close medical surveillance for at least 60 hours. The subjects will then be allowed to leave the trial site after formal assessment and confirmation of their fitness. On all other study days, subjects will be treated in an ambulatory fashion.

For details on time points and procedures for BI 730357 dosing, collection of plasma and urine samples for PK analysis, refer to the [Flow Chart](#) and Section [5.3.2](#).

The safety measurements performed during the treatment period are specified in Section [5.3](#) of this protocol and in the Flow Chart. For details on times of all other trial procedures, refer to the Flow Chart. AEs and concomitant therapy will be assessed continuously from screening until the end of trial examination but will specifically asked for at the timepoints specified in the Flow Chart.

